The dose of SAR442720 will be escalated or de-escalated depending on the emerging safety data of the combination. The starting dose (dose level 1 [DL1]) of SAR442720 will be 100 mg BIW, which is 50% of the highest cleared dose in the ongoing Phase 1 monotherapy dose escalation study (<https://clinicaltrials.gov>; NCT03634982). DL2 (140 mg BIW) and DL 3 (200 mg BIW) for SAR442720 have been cleared in the ongoing Phase 1 monotherapy dose escalation study. The adagrasib starting dose (DL1) will be 400 mg BID orally, which is one dose level below the RP2D in monotherapy (3). Refer to [Table 14](#) below for dose escalation. At least 6 participants need to be treated at the MTD and RP2D.

Table 14 - Dose escalation for Part-3A

Dose Level	SAR442720 (BIW)	Adagrasib (daily)
Part-3 – DL(-)1	80 mg D1, D2	400 mg BID
Part-3 – DL1 (starting dose)	100 mg D1, D2	400 mg BID
Part-3 – DL2	140 mg D1, D2	400 mg BID
Part-3 – DL3a ^a	140 mg D1, D2	600 mg BID
Part-3 – DL3b ^a	200 mg D1, D2	400 mg BID
Part-3 – DL4	200 mg D1, D2	600 mg BID

Abbreviations: BID, twice daily; BIW, twice a week; D, day; DL, dose level.

^a DL3b is optional and may be recommended by the study committee according to the safety data before further escalating to DL4.

Overall safety monitoring will be performed throughout the conduct of the study. Additional dose levels and/or additional schedules of administration can be tested based on emerging PK and safety data.

The DLT observation period is 1 cycle (21 days). All the AEs occurring during treatment, unless due to disease progression or to a cause obviously unrelated to IMP, will be taken into consideration by the Sponsor and recruiting Investigators for the determination of the MTD and RP2D for the SAR442720 and adagrasib combination. The Study Committee will review the overall safety, PK/PD, and clinical activity data and in agreement with the Sponsor's Study Medical Manager, will decide the recommended dose for the expansion phase.

The Study Committee will be comprised of the Principal Investigator from each site involved in the dose escalation phase, clinical team members from the Sponsor (including at least the Study Medical Manager, Global Study Manager, and experts when appropriate such as Global Safety Officer, pharmacokineticists, and biostatisticians).

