6.1 STUDY INTERVENTION(S) ADMINISTERED

Table 16 - Overview of study interventions administered in Part-1, -2, and -4

Study Intervention name	SAR442720		Pembrolizumab
Type	Drug		
Dose formulation	Powder-in-capsule	Film-coated tablet	Lyophilized powder in single-dose vial for reconstitution or solution in a single-dose vial
Unit dose strengths	20 mg and 100 mg		50 mg/vial or 100 mg/4 mL (25 mg/mL)
Dosage levels	The starting dose depends on which combination is evaluated		200 mg Q3W or 400 mg Q6W (for Part-2)
Route of administration	Oral with water after 1 hour fast; no food or drink (other than water) allowed for 1 hour after administration		Intravenous infusion over 30 minutes in accordance with the product leaflet
Use	Experimental combination		
IMP and NIMP	IMP		
Packaging and labeling	SAR442720 capsule will be provided in 8-count HDPE bottles	SAR442720 tablets will be provided in a wallet containing 1 Aclar blister of 8 tablets	Pembrolizumab will be provided in 50 mg lyophilized powder in single-dose vial for reconstitution or 100 mg/4 mL (25 mg/mL) solution in a single-dose vial
	Each bottle will be labeled as required per country requirement	Each wallet will be labeled as required per country requirements	Each box will be labeled as required per country requirement
Current/Former names or aliases	SAR442720, RMC-4630, RMC 0694630	SAR442720	KEYTRUDA®, pembrolizumab

Abbreviation: BID = twice daily; BIW = Day 1 and Day 2 of each week, Day 1 and Day 4 of each week, or any other emergent dose schedule from the ongoing Phase 1 monotherapy escalation study; HDPE, high-density polyethylene, IMP, investigational medical product; NIMP, noninvestigational medical product; Q3W = once every 3 weeks; Q6W, Q3W = once every 3 weeks.

Table 17 - Overview of study interventions administered in Part-3

Study Intervention name	SAR442720	Adagrasib
Type	Drugs	
Dose formulation	Powder-in-capsule	Film coated tablets
Unit dose strengths	20 mg and 100 mg	200 mg
Dosage levels	The starting dose depends on which combination is evaluated	400 mg BID or 600 mg BID; should be at 12-hour intervals to the extent possible
Route of administration	Oral with water after 1 hour fast; no food or drink (other than water) allowed for 1 hour after administration	Oral with at least 240 mL (8 ounces) of water; may be taken with or without food
Use	Experimental combination	
IMP and NIMP		IMP

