6.6.1 Dose modification criteria

6.6.1.1 General guidelines for adagrasib (Part-3)

The following are the general guidelines for withholding, resumption or re-challenge of treatment with adagrasib:

- following adagrasib dose reduction and control of an AE, re-challenge at a higher adagrasib dose may be permitted after discussion with the Sponsor;

- if resumption of dosing for adagrasib is delayed for ≥ 14 days due to an AE that is at least suspected to be attributable to study treatment, then resumption at a reduced dose should be considered;
- if treatment with adagrasib is withheld for ≥ 22 consecutive days, then permanent discontinuation from treatment with one or both agents should be considered; and
- if a treatment-related AE recurs despite dose reduction of adagrasib to the lowest dose anticipated, then permanent discontinuation from study treatment should be considered, unless after discussion with the Sponsor it is considered to be in the best interest of the participant to continue.

Treatment interruptions and modification guidelines are provided in Appendix 9 ([Section 10.9](#)).

Additional guidelines for adagrasib:

Hepatic Toxicities

Hepatic toxicities that are considered to be causally related to adagrasib should initially be managed with treatment interruption of one or both study drugs as outlined in [Table 27](#). Evaluations for confounding factors (eg, cholestasis, metastasis, or viral infection) should be performed as clinically indicated, and more frequent monitoring of a hepatic panel (including AST, ALT, alkaline phosphatase, and bilirubin) should be considered for those participants with transaminase increases. Following resolution of toxicity to the specified degree, dose reduction of adagrasib should be implemented.

Other Laboratory Investigation-Based Toxicities

Other laboratory investigation-based toxicities that are considered to be causally related to adagrasib should initially be managed with treatment interruption of adagrasib as outlined in [Table 27](#). Following resolution of toxicity to the specified degree, dose reduction of adagrasib should be implemented.

Cardiac Toxicities

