Hepatitis, liver function test abnormalities (AST, ALT, and/or total bilirubin)	
Grade 1: Continue both study drugs at current doses.
 
Grade 2: In Part-1, 2, and 4, continue SAR442720 and withhold pembrolizumab until adverse reactions recover to Grade 0 to 1
 
In Part-3, continue SAR442720 and reduce adagrasib one dose level.
 
Grade 3: Rule out other causes such as metastatic liver disease, concomitant drugs, infection, etc. Withhold both study drugs until improves < Grade 1, then dose reduce SAR442720 and adagrasib one dose level (in Part-3) and resume pembrolizumab at the same dose (Part-1, 2 and 4). If AE does not improve or recurs, dose reduce another dose level of SAR442720. No dose modification required for isolated GGT. In Part-1, 2, and 4 hold SAR442720; if no improvement in LFTs after SAR442720, withhold pembrolizumab as well. If Grade ≥ 3 with AST or ALT occurs, permanently discontinue both study drugs.
 
In case of liver metastasis with baseline Grade 2 elevation of AST or ALT, hepatitis with AST or ALT increases $\geq 50\%$ and lasts ≥ 1 week: Permanently discontinue pembrolizumab. Action with SAR442720 or adagrasib should be discussed with the Medical Monitor.
 
Grade 4: see general Grade 4 non-heme AEs. In Part-1, 2, and 4 hold both SAR442720 and pembrolizumab. If resolves, restart both medications, SAR442720 at reduced dose (pembrolizumab dose reduction is not allowed). If no improvement to < Grade 1 within 4 weeks, permanently discontinue both drugs.
 
In Part-3 permanently discontinue both study drugs. Concurrent treatment-emergent / treatment related elevation of AST or ALT $> 3 \times$ ULN AND total bilirubin $> 2 \times$ ULN or INR > 1.5 in the absence of cholestasis and other causes (eg, viral hepatitis, other pre-existing or acute liver disease, or another drug capable of the observed injury), which may indicate severe drug-induced liver injury (possible Hy's law case). Both medications should be permanently discontinued.
 
If liver injury is due to other causes such as viral hepatitis, acute liver disease, or another drug capable of liver injury, evaluate the extent of liver injury (eg, albumin level, PTT, INR etc) and if considered to be severe, discontinue both medications.

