QTcF prolongation	
Rule out other factors for arrhythmia including myocardial ischemia, electrolyte abnormalities, and concomitant medications. Evaluate concomitant medications that prolong QTcF (eg, 5-HT3 receptor antagonist anti-emetics etc) and discontinue the suspected concomitant medication, as feasible. Hold discontinue both study drugs per below instructions. Consult cardiology.
 
Grade ≥ 3: Hold both study drugs until QTcF < 480 msec; correct electrolytes; consult cardiology. If resolves within 4 weeks, restart both drugs; SAR442720 and adagrasib at one dose level lower (pembrolizumab dose reduction is not allowed); otherwise permanently discontinue.
 
Repeat ECG at 2 weeks and 4 weeks after restarting. Perform additional ECGs monitoring at D15 of each subsequent cycle for 3 cycles then as instructed by the SoA. For recurrence of QTc prolongation follow the guidelines above and reduce dose of SAR442720 and adagrasib by another dose level (pembrolizumab dose reduction is not allowed). Permanently discontinue both SAR442720 and pembrolizumab if after correction of associated risk factors and dose reductions, the QTcF increase meets values of both > 500 msec and > 60 msec change from pre-treatment values.
 
In Part-3: If QTcF Prolongation* > 500 msec and increases by > 60 msec on at least 2 ECGs ≤ 22 days, hold adagrasib until \leq Grade 1 or return to baseline (< 15 msec above baseline). Resume adagrasib at one or two dose levels lower. If QTcF Prolongation* > 500 msec and increases by > 60 msec on at least 2 ECGs > 22 days, discontinue adagrasib.

AE	Action

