#### Part-3

Part-3 of this open-label, multi-center, un-controlled, non-randomized study, will assess the safety, RP2D, anti-tumor activity, and PK of SAR442720 in combination with adagrasib in participants with NSCLC harboring KRAS G12C mutation.

Part-3A of the study will investigate the safety and tolerability of SAR442720 in combination with adagrasib and confirm RP2D. There are 6 dose levels in consideration: the starting dose (dose level 1 [DL1]) of IMP combination will be 100 mg BIW and 400 mg BID for SAR442720 and adagrasib respectively, dose level 2 (DL2) will be 140 mg BIW and 400 mg BID, dose level 3a (DL3a) will be 140 mg BIW and 600 mg BID, dose level 3b (DL3b) will be 200 mg BIW and 400 mg BID, dose level 4 (DL4) will be 200 mg BIW and 600 mg BID, and dose level (-1) ([DL-1]) will be 80 mg BIW and 400 BID. A minimum of 3 DLT evaluable participants for each dose level is required. The DLT observation period is 1 cycle (21 days). The Study Committee will review the overall safety, PK/PD, and clinical activity data and in agreement with the Sponsor's Study Medical Manager, will decide the recommended dose for the expansion phase.

Part-3B dose expansion will assess the anti-tumor activity and safety of SAR442720 combined with adagrasib in participant with NSCLC harboring KRAS G12C mutation. This study will start once RP2D for SAR442720 and adagrasib from Part-3A dose escalation is confirmed. Approximately 40 participants will be enrolled.

Part-4 of this study will assess the effect of food on PK of SAR442720 tablet, when dosed in combination with pembrolizumab in participants with advanced malignancies. It will also evaluate the relative bioavailability of SAR442720 tablet formulation (test) compared to the capsule formulation (reference) when dosed in combination with pembrolizumab. Approximately 12 participants are expected to be enrolled.

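### Table 27 calls for adagrasib reductions of one or more dose levels, but neither document defines a dose below the 400 mg BID starting dose

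*Protocol*

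**What the plan says.** **Doses defined.** Protocol Table 17 (Section 6.1) gives the adagrasib dosage as "400 mg BID or 600 mg BID; should be at 12-hour intervals to the extent possible". Section 4.1 states "The adagrasib starting dose (DL1) will be 400 mg BID orally" and places this one level below the monotherapy RP2D. Table 14 uses no other adagrasib dose. The SAP description of Part-3 says "There are 6 dose levels in consideration" and lists the same six combinations.

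**Reductions called for.** Table 27 contains these Part-3 instructions for adagrasib:

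- Liver tests: at Grade 2, "continue SAR442720 and reduce adagrasib one dose level"; at Grade 3, one level for both drugs.
- QTcF: at Grade 3 or above, restart one level lower. On recurrence, "reduce dose of SAR442720 and adagrasib by another dose level". For QTcF above 500 msec with an increase above 60 msec, lasting up to 22 days, "Resume adagrasib at one or two dose levels lower".
- Febrile neutropenia and Grade 4 cytopenias: one level lower.
- Other cardiac events of Grade 3 or above, and Grade 4 hypertension: adagrasib may resume one level lower.
- Pneumonitis: at Grade 1, consider one level lower; at Grade 2, one level lower if resumed.
- Diarrhea: reduce the dose, with no number of levels given.

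**Supporting sections.** The Part-3 paragraph opening Section 6.6 gives a reduction step for SAR442720 only. Section 6.6.1.1 says adagrasib should be reduced after several kinds of toxicity, but gives no dose. It makes recurrence despite "dose reduction of adagrasib to the lowest dose anticipated" a reason to consider permanent discontinuation, without saying what that dose is.

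**The concern.** Part-3A starts at the lower of the two defined adagrasib doses. A site that follows Table 27 after a hepatic or QTcF event at that dose is told to step down, but the documents give it nothing to step down to.

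These events are foreseeable. Section 2.3.1.4 reports, among events attributed to adagrasib across all patients, ALT increase in 16.2%, AST increase in 14.7% and QT prolongation in 10.8%. Section 2.3.1.5 says more frequent QT prolongation with the combination cannot be excluded. These percentages cover all grades, so they are not rates of events that would trigger a reduction.

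What is at stake is consistent safety management after a toxicity and, with it, comparable adagrasib exposure from then on among participants assigned to the same dose level.

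**Working it through.** No sample-size or power formula applies. The check is a count of dose levels against the reductions called for.

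**The plan's own figures.** The SAP's six levels match the six rows of Protocol Table 14. Section 4.2 describes the adagrasib starting dose as two thirds of its RP2D: 400 / 600 = 0.667, which agrees.

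**The adagrasib ladder.** The distinct adagrasib doses in Table 14 are 400 mg BID (rank 1) and 600 mg BID (rank 2). A reduction of k levels from rank r has a defined target only if r − k ≥ 1.

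| Level (Table 14) | SAR442720, D1 and D2 | Adagrasib BID | Rank r | r − 1 | One level lower | r − 2 | Two levels lower |
|---|---|---|---|---|---|---|---|
| DL(-)1 | 80 mg | 400 mg | 1 | 0 | none defined | −1 | none defined |
| DL1 (start) | 100 mg | 400 mg | 1 | 0 | none defined | −1 | none defined |
| DL2 | 140 mg | 400 mg | 1 | 0 | none defined | −1 | none defined |
| DL3a | 140 mg | 600 mg | 2 | 1 | 400 mg BID | 0 | none defined |
| DL3b (optional) | 200 mg | 400 mg | 1 | 0 | none defined | −1 | none defined |
| DL4 | 200 mg | 600 mg | 2 | 1 | 400 mg BID | 0 | none defined |

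One level lower has no defined target at 4 of 6 levels. Two levels lower, or a further level after a first reduction, has none at 6 of 6.

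**Sensitivity to which levels are counted.** Section 4.1 assumes five combination levels. Leaving out DL(-)1, the one-level count is 3 of 5 (DL1, DL2, DL3b). Leaving out optional DL3b as well, it is 2 of 4 (DL1, DL2). The starting dose is affected in every version.

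**Alternative reading: a dose level means the combination level.** Stepping down the rows of Table 14 changes adagrasib as follows:

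- DL1 to DL(-)1: 400 to 400
- DL2 to DL1: 400 to 400
- DL3b to DL2: 400 to 400
- DL4 to DL3a: 600 to 600
- DL3a to DL2: 600 to 400
- DL4 to DL3b: 600 to 400

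From every level on 400 mg BID that has a level below it, adagrasib is unchanged, and below DL(-)1 nothing is listed. The Grade 2 liver rule also lowers adagrasib while SAR442720 continues, and Section 4.1 places 400 mg BID one level below the monotherapy RP2D. Both treat adagrasib as having levels of its own.

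**The case against.** The strongest reply is that Table 27 is not a set of orders. Appendix 9 presents it as guidance subject to the physician's clinical judgment. The rows for other cardiac events, Grade 4 hypertension and pneumonitis are permissive, and several rows send unclear or individual cases to the Medical Monitor. Section 6.6.1.1 provides for discussion with the sponsor on re-challenge and on continuing after recurrence. Section 6.1.1 refers to a Pharmacy Manual that is not available here. Adagrasib comes as 200 mg tablets, so smaller amounts could be dispensed.

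Much of this stands, and it rules out several stronger readings that a reader might infer:

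- **That the toxicity rule cannot be carried out.** What the documents show is that no target dose is defined. Differing practice between sites is a plausible consequence, not something they demonstrate.
- **That the rule for QTcF above 500 msec fails at every level.** It offers one level or two, so at 600 mg BID it can be met with one.
- **That the discontinuation trigger in Section 6.6.1.1 is unusable.** It asks only that discontinuation be considered. After a reduction from 600 to 400 mg BID it can be applied if 400 is taken as the floor. It is undefined for participants on 400 mg BID for whom a further reduction is called for.
- **That all of the roughly 40 Part-3B participants would be affected.** Only those with a toxicity calling for an adagrasib reduction would meet the gap.

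The core remains. Clinical judgment and a call to the Medical Monitor do not supply a dose level that the plan refers to but does not list. The wording for liver tests, Grade 3 or higher QTcF, febrile neutropenia and Grade 4 cytopenias is direct. A tablet strength is not a dose level. No redaction falls in Table 14, Table 17 or Section 6.6.1.1.

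**Conclusion.** The point holds as an internal inconsistency, not as a criticism of a design choice. Table 27 directs or permits adagrasib reductions below 400 mg BID, and Section 6.6.1.1 relies on a lowest dose; the protocol and SAP define neither. The one-level step lacks a target at four of the six listed levels, including the starting dose, and a second step lacks one at all six.

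This rests on reading an adagrasib dose level as a dose listed in Table 14 or 17, and on no further steps being set in a document not seen here. If the RP2D carries 400 mg BID, the gap extends to any Part-3B participant with a toxicity that calls for adagrasib reduction. The documents give no basis for estimating that number. The matter should be settled because it affects safety management at the trial's own starting dose and is cheap to correct.

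**What to change.** Reconcile Table 27 and Section 6.6.1.1 with Tables 14 and 17 in one of two ways:

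- state the adagrasib reduction steps and the lowest dose, preferably beside Table 14; or
- state the instruction that applies to a participant on 400 mg BID when Table 27 calls for a reduction.

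In either case, make clear what a further level means on QTc recurrence, and how the diarrhea row, which gives no number of levels, is to be read. The sponsor's clinical team must set the content; no dose or clinical rule is proposed here. The cost is protocol wording or a clarification letter, with no change to sample size or planned analyses.

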Hematologic lab abnormalities > Grade 3	
Assess for other causes. Hold concomitant medications associated with myelosuppression.
 
Grade 3 neutropenia, thrombocytopenia: Hold both drugs if clinically indicated until $<$ Grade 1 or baseline. If improves within 4 weeks, restart pembrolizumab or adagrasib at same dose and administer SAR442720 one dose level lower. If does not improve within 4 weeks, discontinue both drugs.
 
Grade 3 febrile neutropenia: Hold both drugs until fever resolves and ANC $<$ Grade 1 or baseline. If improves within 2 weeks, restart pembrolizumab at same dose and SAR442720 and adagrasib 1 dose level lower. If does not improve within 2 weeks, discontinue both drugs.
 
Grade 3 anemia: Assess transfusion history. Transfuse per institutional guidelines. Continue pembrolizumab, and hold SAR442720 if clinically indicated until $<$ Grade 1. If improves within 4 weeks, restart SAR442720 one dose level lower. If does not improve within 4 weeks, consider discontinuation of both drugs. Hold adagrasib until \leq Grade 1 or baseline and may resume at the same dose level.
 
Grade 4 cytopenias: Hold both drugs until resolves to $<$ Grade 1 or baseline. If improves within 4 weeks, restart both drugs; reduce both SAR442720 and adagrasib one dose level lower (pembrolizumab dose reduction is not allowed). If does not improve within 4 weeks, discontinue both drugs.
 
Thrombocytopenia associated with clinically significant bleeding, at any level: Hold both drugs and follow hemorrhage recommendations.
 
Uncomplicated Thrombocytopenia (without clinically significant bleeding):
 
Grade 1 to 2: Continue treatment at current dose level and frequency and monitor closely
 
Grade 3 to 4: Manage per institution guidelines and interrupt dosing of both study drugs until participant recovers to Grade 1 or better. If recovery occurs, the investigator may resume dosing both study drugs at the same dose level and frequency, if clinically appropriate. If Grade 3 to 4 events recur again, hold dose until recovery to Grade 1 or better and consider re-introducing study drug at reduced frequency, or withdrawing participant from study therapy.
 
Please contact Medical Monitor for ambiguous cases.

AE	Action

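### Table 27 gives two overlapping instructions for Grade 3-4 thrombocytopenia without significant bleeding; they conflict on the 4-week stop and omit Table 11's bleeding-risk condition

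*Protocol*

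**What the plan says.** All of the following stands in the hematologic row of Protocol Appendix 9, Table 27.

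- **Grade 3 line (neutropenia, thrombocytopenia).** Hold both drugs if clinically indicated. On improvement within 4 weeks, "restart pembrolizumab or adagrasib at same dose and administer SAR442720 one dose level lower". Otherwise: "If does not improve within 4 weeks, discontinue both drugs".
- **Grade 4 cytopenia line.** Hold both drugs. On improvement within 4 weeks, "reduce both SAR442720 and adagrasib one dose level lower", with pembrolizumab unchanged. The same 4-week discontinuation follows.
- **Significant bleeding.** Thrombocytopenia with clinically significant bleeding goes to the hemorrhage recommendations.
- **Uncomplicated block.** It is headed "Uncomplicated Thrombocytopenia (without clinically significant bleeding"). At Grade 3 to 4, "interrupt dosing of both study drugs until participant recovers to Grade 1 or better"; after recovery, "the investigator may resume dosing both study drugs at the same dose level and frequency, if clinically appropriate". If the event recurs, hold again and consider a reduced frequency or withdrawal. No time limit is given.
- **End of row.** "Please contact Medical Monitor for ambiguous cases".

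Protocol Table 11 (Section 2.3.1.1) gives the same interrupt-and-resume advice but defines uncomplicated more narrowly: it also excludes significant bruising and other known bleeding-risk factors. For bleeding events, or for participants whose additional risk factors are significant, it says the general dose modification guidelines should be considered.

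Protocol Section 6.6.1.1 (Part-3 only) adds advice on adagrasib. A reduced dose should be considered after a delay of 14 days or more for a suspected related event. Permanent discontinuation of one or both agents should be considered after 22 or more consecutive days withheld.

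**The concern.** Nothing in the row says whether the uncomplicated block replaces the Grade 3 and Grade 4 lines or sits beside them. A site managing a platelet count in the Grade 3-4 range without bleeding can find its patient under both, and two sites can follow different stop rules and restart doses for the same event. Grade 3 or higher thrombocytopenia is a listed potential risk (Table 11) and an adverse event of special interest (Section 8.3.6).

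The second strand is the lost condition. Investigators will work from Table 27 when they restart treatment, and its definition of uncomplicated mentions only bleeding. A participant with significant additional bleeding-risk factors who is not bleeding therefore qualifies, without any qualification, for same-dose restart of both drugs.

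**Working it through.** The check is mainly a comparison of text.

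**1. Which cases fall where.** Significant bleeding leaves the row for the hemorrhage recommendations. Every other Grade 3-4 platelet event meets the block's heading. The Grade 3 and Grade 4 lines are not limited to any subgroup, so they cover the same events.

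| | Grade 3 / Grade 4 lines | Uncomplicated block |
|---|---|---|
| Hold | Grade 3: if clinically indicated; Grade 4: hold both | Interrupt both |
| SAR442720 restart | One level lower | Same dose permitted |
| Adagrasib restart | Same at Grade 3; one level lower at Grade 4 | Same dose permitted |
| Not improved at 4 weeks | Discontinue both | Nothing stated; hold until recovery |
| Recurrence | Nothing stated | Hold; consider reduced frequency or withdrawal |

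**2. Can one action satisfy both?** On restart dose, yes: the block permits the same dose but does not require it, so lowering SAR442720 (and adagrasib at Grade 4) complies with both. On the stop rule, no: for a participant still unrecovered at 4 weeks, one instruction is to discontinue and the other is to go on holding.

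**3. Does anything settle precedence?** If the block always overrode the general lines, the word thrombocytopenia in the Grade 3 line and the platelet part of the Grade 4 line would have no cases left. Table 11's narrower definition would leave them some: bruising or bleeding-risk cases without significant bleeding. Table 27 does not carry that definition. The most-conservative rule at the start of Appendix 9 is for several adverse events in one participant, not one event under two lines. The Medical Monitor sentence names whom to ask, not which rule applies.

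**4. Size per participant.** Dose levels are from Tables 13 and 14; Part-2 uses 200 mg twice weekly (Section 4.1).

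- 200 to 140 mg: 2 × 200 = 400 against 2 × 140 = 280 mg per week; 120/400 = 30.0% lower.
- 140 to 100 mg: 40/140 = 28.6% lower.
- 100 to 80 mg: 20/100 = 20.0% lower.
- Adagrasib 600 to 400 mg BID: 200/600 = 33.3% lower.

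**5. How often, as context only.** Table 11 reports 17/113 = 15.0% with Grade 3-4 events in the monotherapy study; the exact (Clopper-Pearson) 95% CI is 9.0% to 23.0%. If that rate carried over:

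- 20 participants: 20 × 0.150 = 3.0 (1.8 to 4.6).
- 40 participants: 40 × 0.150 = 6.0 (3.6 to 9.2).

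**6. Could the 4-week stop bind?** Table 11 gives a median thrombocytopenia duration of 24.0 days, against 28 days for the stop. That median is not specific to Grade 3-4, so it yields no rate, but it shows the stop could matter.

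**The case against.** The best defence is that a workable reading exists. The block is the more specific rule and repeats Table 11's advice, and Section 2.3.1.1 says thrombocytopenia is managed mainly by interrupting doses. Same-dose restart may therefore be what the sponsor intends for truly uncomplicated cases. Appendix 9 calls its tables guidelines subject to clinical judgment, the same-dose line is optional, and ambiguous cases can go to the Medical Monitor. Table 11 also reports no Grade 3-4 bleeding in conjunction with thrombocytopenia at the data cutoff.

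Most of this stands, and it limits the point in three ways:

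- A reader might infer that the two instructions force opposite restart doses. They do not, because the same-dose option is permissive.
- A reader might infer that the block is laxer throughout. It is stricter on holding at Grade 3 and has a recurrence step that the thrombocytopenia lines lack. In Part-3 it also operates alongside the advisory 14-day and 22-day adagrasib limits, so no time limit is true of the block itself but not of all the Part-3 guidance.
- A reader might infer that Table 11 bars same-dose restart for anyone with a bleeding-risk factor. It refers only to significant additional risk factors, and says only that the general guidelines should be considered.

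The defence does not supply a statement of precedence, reconcile the 4-week stop, or explain why Table 27's definition is wider than Table 11's.

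**Conclusion.** The point holds as a modest safety and consistency issue that should be corrected. Two things are established from the text. The 4-week stop applies under one instruction and not the other for the same event. Table 27 also permits same-dose restart, without qualification, in participants with significant additional bleeding-risk factors whom Table 11 treats separately.

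Where the restart doses diverge, the gap is 20% to 30% of the SAR442720 dose and, at Grade 4 in Part-3, 33% for adagrasib stepping down from 600 mg. The counts of about 3 per 20 or 6 per 40 assume the monotherapy rate carries over. They are neither a forecast nor a ceiling: the rate pools all monotherapy dosing cohorts, the intermittent schedule may be better tolerated than daily dosing (Section 2.3.1.1), and adagrasib may raise SAR442720 exposure up to 2-fold (Section 2.3.1.5). The documents do not give the share with significant bleeding-risk factors or the share unrecovered at 4 weeks.

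Two further inferences are tempting but not supported. Table 26 might seem to add a third outcome, but Appendix 9 assigns specific events to Table 27, and Table 26's cells are incomplete as printed. The recovery thresholds in the two parts of the row differ in print, but that may be only a symbol error. No endpoint definition or planned analysis changes.

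**What to change.** 1. In Table 27, define uncomplicated as in Table 11: no clinical bleeding, no significant bruising and no significant additional risk factors for bleeding. Use that one risk-factor threshold in both tables. Table 11 now uses a broader one in its definition (any other known risk factor) than in its routing sentence. Copying the broader one could withdraw the same-dose option from participants Table 11 does not send elsewhere, for example if low-dose aspirin or the anticoagulants allowed by Section 6.5 were counted.
2. Add one sentence of precedence. The uncomplicated block replaces the Grade 3 and Grade 4 lines for platelet events meeting that definition; those lines apply to other platelet events without clinically significant bleeding; clinically significant bleeding follows the hemorrhage row.
3. State whether the 4-week stop applies to the uncomplicated block.

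The cost is wording in one row of Table 27 and a matching edit in Table 11, largely from the sponsor's own text. Sample size, visits and analyses are unaffected, and same-dose restart stays available for cases that are truly uncomplicated.
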